7.3.1 Variables Operational Definition

Table 7.1 Dependent Variable

No.	Variable	Definition	Measured with	Scoring	Scale
1	In-hospital mortality	Patient dies in hospital during treatment after cardiac surgery (patient has never gone home or been discharged from hospital)	Medical record	0 = Not Died 1 = Died	Categorical

Table 7.2 Independent Variables

No.	Variable	Definition	Measured with	Scoring	Scale
1	Acute Kidney Injury	Patients with an increase in serum creatinine more than 1.5 times or > 0.3 mg/dL with urine output < 0.5 cc/kg/hour for 6 consecutive hours.	Medical record	0 = No AKI 1 = With AKI	Categorical
2	Renal Replacement Therapy	Use of a renal replacement therapy machine, either continuous (CVVH) or intermittent (HD), during the period the patient is treated post-operatively until discharge from the hospital.	Medical record	0=Not required 1=Required	Categorical
3	Age	calculated from the day of birth to the day the surgery was performed in years	Medical record	0 = ≤ 60 years 1 = > 60 years	Categorical

		These are surgical procedures undertaken by patients, divided into 5 categories:		
4	Type of valve surgery	1. Coronary Artery Bypass Graft (CABG) is a coronary heart bypass surgery	1 = CABG	
		2. Valves or heart valve surgery is surgery performed on heart valves	2 = Valves	
		3. Mixed valves are heart valve surgery performed simultaneously with other heart surgical procedures (for example coronary or vascular)	3=Mixed Valves	Categorical
		4. Congenital is surgery for congenital heart defects suffered by the patient	4= Congenital	
		5. Other is for surgery that is not included in the 4 categories above (for example Vascular)	5 = Others	
5	Diabetes Mellitus	Obtained from the history of the disease suffered and blood sugar laboratory results.	Medical record	0= No 1= Yes
6	Hypertension	Obtained from the history of the disease suffered by the patient/which was diagnosed	Medical record	0= No 1= Yes

		before undergoing surgery, where the increase in systolic blood pressure is above the normal limit, namely more than 140 mmHg and diastolic blood pressure is more than 90 mmHg.			
7	Serum Creatinine	Serum creatinine value > 3.0 obtained last before surgery, in mg/dL	Medical record	0= No 1= Yes	Categorical
8	History of Stroke	History of stroke diagnoses that the patient has experienced, either with or without sequelae	Medical record	0= No 1= Yes	Categorical

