[name], MD	Address: [name] [contact] [name] Email : [contact]

Contributing Investigators

1. [name] MD Address:Department of Perioperative Intensive Care and Non-Surgical Anaesthesia
[name]
ORCID ID : [name]
2. [name] MD. Address:Department of Perioperative Intensive Care and Non-Surgical Anaesthesia
[name]
ORCID ID : [name]
3. [name] MD Address:Department of Perioperative Intensive Care and Non-Surgical Anaesthesia
[name]
ORCID ID : [name]
4. [name] MD Address:Department of Perioperative Intensive Care and Non-Surgical Anaesthesia
[name]
ORCID ID : [name]

4 Abstract

The prevalence of acute kidney injury (AKI) varies up to 30% in post-cardiac surgery patients. Of the patients who suffer from AKI, around 1 - 10% will require renal replacement therapy (RRT). Cardiac surgery associated-AKI patients who require renal replacement therapy/dialysis have higher risk of mortality. The purpose of this study was to assess the risk of AKI-RRT on intrahospital mortality, and other factors that have an association with postoperative mortality. The method was non-experimental research design as retrospective cohort analysis. Dependent variable, in-hospital mortality was determined first and then the independent variables were examined to see the relationship between the variables.

Keywords: Acute Kidney Injury (AKI), Renal Replacement Therapy (RRT), cardiac surgery, intrahospital mortality

5 Rational and Background

The overall incidence of mortality post-cardiac surgery in some literatures varies between 2-8%. Cardiac surgery associated - acute kidney injury (CSA-AKI), a common postoperative complication, has increased risk for post-operative mortality. The incidence of mortality in patients complicated with CSA-AKI is up to 60%. The most severe stage of CSA-AKI, which requires dialysis therapy, is an independent risk factor. The prevalence of acute kidney injury is ranged up to 28% in cardiac surgery patients, of which around 1 – 10% of those patients required renal replacement therapy (RRT).¹⁻⁵

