7.2.1 Study Population

Target population for this study is patient aged at least 18 years, who experienced cardiac surgery at adult cardiac surgical unit at tertiary cardiac center from January 2020 to December 2022.

The study population will be identified according to the below inclusion and exclusion criteria.

Inclusion Criteria:

The patient can be included in the study when:

- Data on patients who are at least 18 years old, who experienced cardiac surgery at our tertiary cardiac center from January 2020 to December 2022.

- Data on post-cardiac surgery patients who complicated with Acute Kidney Injury (AKI) which was characterized by an increase in serum creatinine $> 0.3 \text{ mg/dL}$ or $> 150\%$ of the pre-operative serum creatinine level, which was checked within 12 hours post-surgery.
- Data is available in the medical records unit of the Harapan Kita National Heart Center.

Exclusion Criteria:

The patient cannot be included when the patient

- Patients with a previous history of dialysis.
- Data on patients who underwent surgery outside the specified period

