7.3 Variables

The data collected from EMR included demographic data (age, weight, height, sex), type of surgery, comorbidities (history of diabetes, hypertension, stroke, smoking, renal disease), creatinine level, duration of mechanical ventilation, and ICU length of stay. Clinical variables are obtained that included mechanical ventilation time, ICU length of stay, postoperative diuretic, inotropes, vasopressor therapy, postoperative use of intra-aortic balloon pump (IABP), postoperative RRT, and in-hospital mortality. For the study's purpose, several continuous variables are categorized qualitatively such as mechanical ventilation (>48 hours as a cutoff point), ICU (≥ 5 days), postoperative diuretic therapy (yes/no), inotropes and vasopressor therapy ≥ 2 drugs (yes/no), and postoperative use of IABP (yes/no).

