7.7 Statistical Analysis Plan

All analyses will be performed on patients who underwent cardiac surgery in period between 1 January 2020 until 31 December 2022, with complication of acute kidney injury (AKI) postoperative. All data were retrieved from patient medical record retrospectively. There were no active observation or data retrieved directly from patients.

Data analysis will be carried out by the statistical team after the research samples have been taken and the data has been completed. The analysis was carried out using SPSS Version 29. and all statistical analysis plans have been completely documented in this statistical analysis plan.

Data that has been processed correctly is then analyzed by:

- a. Univariate analysis

This univariate analysis was carried out to obtain an overview of the frequency distribution of research subjects and the distribution of the proportion of cases and controls according to each independent variable (risk factor) studied.

- b. Bivariate analysis

Bivariate analysis was used to determine the relationship between the main risk factors and the incidence of death in hospital while also testing the research hypothesis using the chi square test.

c. Multivariate analysis

Multivariate analysis is carried out with the aim of describing the relationship between the dependent variable and the independent variable simultaneously in the population. Multivariate analysis was carried out by connecting several independent variables with one dependent variable simultaneously. Because the independent variables are categorical, logistic regression was used for the analysis.

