7.7.2 Statistical Methods

The statistical analyses described in this section will be performed as further outlined in the SAP, which will be finalized prior to database lock and will be included in the clinical study report for this protocol. The final SAP will take into account any amendment to the protocol.

General Statistical Methodology:

Descriptive statistics (mean, SD, median, interquartile range) will be provided for continuous variables according to the results of data normality tests. Frequencies and percentages will be presented for categorical and ordinal variables.

All analyzes will consider the security of the dataset.

Primary Outcome Analysis:

The primary outcome in this study is to look at the incidence of death in the treatment of patients who have kidney problems with CRRT or not.

Bivariate analysis was carried out using the chi square/fisher's exact test to see whether there was a difference in the incidence of death in treatment between groups (CRRT vs Non-CRRT)

which was then continued to the multivariate analysis stage if it had a p value <0.25 , multivariate analysis was carried out using regression multiple logistics with a significance level of 0.05 which shows that it is a variable that influences the incidence of death in care.

Secondary Endpoint Analysis:

The secondary outcome in this study is to look at the factors causing CRRT in patients undergoing cardiac surgery with AKI.

Bivariate analysis was carried out using the chi square/ Fisher's exact test to see whether there were differences in patient characteristics between patients who were given CRRT and those who were not, which was then continued to the multivariate analysis stage if it had a p value <0.25 . Multivariate analysis was carried out using multiple logistic regression with The significance level is 0.05 which shows that it is a variable that influences the incidence of CRRT use.

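### No candidate covariate measures how severe the AKI was at cohort entry, so the RRT–mortality odds ratio is open to confounding by severity and the mortality-factor search omits it

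*Combined protocol and SAP*

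**What the plan says.** - **Cohort.** Section 7.7 restricts all analyses to cardiac surgery patients "with complication of acute kidney injury (AKI) postoperative".
- **Entry criterion.** Section 7.2.1 defines AKI by a creatinine increase of more than 0.3 mg/dL, or to more than 150% "of the pre-operative serum creatinine level, which was checked within 12 hours post-surgery".
- **Candidate covariates.** Table 7.2 (Section 7.3.1) is the only coded list of independent variables and has 15 items. Item 1 is AKI, scored "0 = No AKI 1 = With AKI". The only creatinine item is item 7: "Serum creatinine value > 3.0 obtained last before surgery, in mg/dL". No item is an AKI stage, a creatinine rise or ratio, or a graded urine-output measure.
- **Data collected.** Section 7.3 lists "creatinine level, duration of mechanical ventilation, and ICU length of stay", with no time point for the creatinine.
- **Exposure.** Table 7.2 counts RRT "during the period the patient is treated post-operatively until discharge from the hospital".
- **Model.** Section 7.7.2 tests variables one at a time against in-hospital death, "which was then continued to the multivariate analysis stage if it had a p value <0.25". It then fits multiple logistic regression at the 0.05 level and reads a significant term as one that has an influence on death. No matching, stratification or propensity method is planned.
- **Role of severity.** Section 5 states: "The most severe stage of CSA-AKI, which requires dialysis therapy, is an independent risk factor". The Study Rationale adds that mortality risk rises several-fold once AKI is severe enough to need RRT.

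**The concern.** The protocol's own background makes AKI severity a likely common cause of RRT and of death. The plan nevertheless treats a patient just over the 0.3 mg/dL threshold and a patient with a three-fold rise as alike. Pre-operative creatinine does not separate them, because two patients with the same pre-operative value can have very different rises.

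Two results are affected:
- **Primary comparison.** The RRT odds ratio may carry excess mortality from patients whose AKI was already worse before RRT. The study could not then say whether needing RRT marks risk beyond the injury present at entry.
- **Third secondary objective (Section 6.2).** Perioperative factors for death in AKI patients would be sought without any measure of how severe the AKI was.

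**Working it through.** The plan states no sample size, power or effect size on this point (Section 7.5 fixes the study by calendar time), so there is no figure of the plan's own to reproduce.

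**1. Can the AKI item adjust for anything?** Every analysed patient has AKI = 1. The design matrix [intercept, AKI] then has two identical columns and rank 1, so the AKI coefficient cannot be estimated.

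**2. Could the entry rise be derived?** Section 7.2.1 needs a pre-operative creatinine and one checked within 12 hours after surgery, so both values should exist for patients admitted under it. Two passages limit this. Section 7.3 does not say that the post-operative value is kept. Table 7.2 defines AKI differently, adding urine output and giving no 12-hour limit.

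**3. Illustration with a continuous severity measure.** The strengths of association are assumptions, because the documents give none.
- Severity Z ~ N(0,1), the standardised log creatinine ratio at entry.
- logit P(RRT | Z) = a + Z·ln(A), with a set so that the overall RRT share is 1%, 5% or 10% (the protocol cites 1–10% of AKI patients).
- logit P(death | Z, RRT) = b + Z·ln(B) + RRT·ln(C), with b set so that mortality without RRT is 8% (assumed).
- The RRT odds ratio that ignores Z is compared with the conditional value C. Inflation is the ratio of the two.

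| A (RRT, per SD) | B (death, per SD) | RRT OR ignoring Z, C = 1 | RRT OR ignoring Z, C = 5 | Inflation |
|---|---|---|---|---|
| 1.2 | 1.1 | 1.02 | 5.08 | about 1.02 |
| 1.5 | 1.3 | 1.11 | 5.46–5.47 | 1.09–1.11 |
| 2.0 | 1.5 | 1.30–1.32 | 6.26–6.32 | 1.25–1.32 |
| 3.0 | 2.0 | 1.90–2.03 | 8.49–8.94 | 1.70–2.03 |

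Ranges run over the three RRT shares.

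**4. Cross-check with a binary severity variable.** Assume 20% severe AKI, RRT 10 times as likely in severe AKI, RRT share 5%, 5% mortality in non-severe patients without RRT, a severity–death odds ratio of 3, and no true RRT association.
- RRT probability: non-severe 0.05/(0.2×10 + 0.8) = 0.0179; severe 0.1786.
- Mortality in severe AKI: odds 3×0.05/0.95 = 0.158, so probability 0.136.
- Severe share: with RRT 0.2×0.1786/0.05 = 0.714; without RRT 0.2×0.8214/0.95 = 0.173.
- Mortality: with RRT 0.714×0.136 + 0.286×0.05 = 0.112; without RRT 0.173×0.136 + 0.827×0.05 = 0.065.
- Odds ratio ignoring severity: 1.81, where the conditional value is 1.0.

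Over RRT 5–20 times as likely, severity odds ratios 2–5 and RRT shares 1–10%, this runs from 1.30 to 2.93. With severity in the model the odds ratio returns to 1.0 by construction.

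**The case against.** - **The objective is an association, and RRT is itself the severity marker.** For a purely prognostic contrast, worse AKI is part of what the RRT group represents, and the estimate without a severity term is a legitimate target. This stands in part, and is why both estimates should be reported. It does not dispose of the point, because Section 7.7.2 plans a multivariable model and gives a significant term an influence reading. Entry severity and RRT at any time until discharge are also different quantities.
- **Other covariates may cover it.** Ventilation, ICU stay, IABP, inotropes and diuretics may absorb part of overall illness severity. They are not graded measures of renal injury, and some may follow RRT. Their net effect on the bias is unknown.
- **The covariate set is not final.** Section 7.7.2 refers to an SAP still to be finalised, while Section 7.7 says the analysis plans are fully documented here. A reader might infer that entry severity is recorded for every patient and is barred from every model. The documents support only that it should be derivable under Section 7.2.1 and that no listed candidate carries it.
- **Limitations are acknowledged.** Section 7.8 mentions predictors of CSA-AKI that could not be included. It does not mention confounding by AKI severity.
- **A 12-hour measure is incomplete.** This stands: AKI that worsens later, before RRT, would remain unadjusted.

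**Conclusion.** The point holds as a gap in the candidate covariates. Following Table 7.2 as written leaves the RRT odds ratio unadjusted for renal severity at entry and leaves the mortality-factor analysis without it. If severity raises the odds of both RRT and death, as the protocol's background implies, omitting it in an otherwise unadjusted comparison pushes the RRT odds ratio upwards.

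The size is not known. A reader might infer that the planned adjusted odds ratio would be inflated by 1.1 to 2.0. The documents do not support that, for three reasons:
- The calculation concerns an RRT odds ratio adjusted for nothing else, while the planned model may include other covariates.
- The associations are assumed. Weak ones (1.2 and 1.1 per SD) give only about 1.02.
- A standard normal severity score ignores that every patient was selected above an eligibility threshold.

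Nor would the added term isolate the effect of RRT. It reduces confounding by indication without removing it.

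**What to change.** 1. **Data (Section 7.3).** Record the post-operative creatinine that established eligibility, with its time, and reconcile the AKI definitions in Section 7.2.1 and Table 7.2.
2. **Table 7.2.** Add AKI severity at entry as a pre-RRT measure, such as the log of the post-operative to pre-operative creatinine ratio, with pre-operative creatinine also in the model as a continuous term. A ratio alone can rank patients with a high baseline as mild: 3.0 to 3.4 mg/dL is a rise of 0.4 and a ratio of 1.13, while 0.8 to 1.25 mg/dL is a rise of 0.45 and a ratio of 1.56. The absolute rise could serve instead as a sensitivity analysis.
3. **Section 7.7.2.** Enter the measure in the mortality model with RRT regardless of the p<0.25 screen, and make it a candidate in the mortality-factor analysis. Report the RRT estimate with and without it.
4. **Section 7.8.** State that a 12-hour measure reduces but does not remove confounding by indication, because RRT is counted until discharge.

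**Cost.** No new patients or procedures. The model gains one or two parameters. Records missing either value may be lost, since Section 7.7.1 leaves missing data out of the analysis. The adjusted RRT odds ratio will probably be smaller.

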6.2 Secondary Objectives

- To analyze the risk of intra-hospital post-surgical mortality in cardiac surgery patients who complicated with CSA AKI
- To compare the risk of intra-hospital post-surgical mortality in cardiac surgery patients who complicated with CSA AKI with requirement of RRT and without RRT
- To Identify and analyze perioperative factors that play an important role in the incidence of mortality in AKI patients after cardiac surgery

7 Research Methods

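### RRT is coded ever/never over the same stay in which death is counted: valid as mortality by RRT received, but open to timing bias if read as an effect and to misclassification if read as RRT requirement

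*Combined protocol and SAP*

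**What the plan says.** Table 7.2 item 2 (section 7.3.1) defines RRT as use of a machine, continuous or intermittent, "during the period the patient is treated post-operatively until discharge from the hospital". It gives no start date and no time limit. The scoring is "0=Not required 1=Required", so the definition speaks of use and the score of need.

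Table 7.1 defines the outcome over the same interval: "Patient dies in hospital during treatment after cardiac surgery", before any discharge.

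Section 7.7 prescribes chi-square and logistic regression. Section 7.7.2 repeats this for the primary outcome, names the groups by CRRT and its absence, and says that a significant variable in the model influences in-hospital death. Neither section has a time axis.

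The stated aims differ in strength. Section 6.1 asks for an association. The first paragraph of section 6 and section 6.2 speak of requirement; section 6.2 compares patients "with requirement of RRT and without RRT". The abstract says "The purpose of this study was to assess the risk of AKI-RRT on intrahospital mortality".

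The variable list in section 7.3 includes ventilation time and ICU stay, which carry some timing, but no date of RRT start, death or discharge. Section 7.8 mentions neither timing nor confounding by indication.

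**The concern.** Exposure is settled by what happens during follow-up. A patient who dies on day 1, or goes home well on day 6, before any RRT, is counted as unexposed for the whole stay. A patient who starts RRT on day 5 is counted as exposed from surgery onward, although that patient had to remain alive and in hospital for the first days to enter the group.

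Two readings in the plan are exposed to this. If the odds ratio is taken as the influence of RRT on death, it mixes mortality with time spent in hospital before RRT could begin. If it is taken as a comparison by need, a patient who needed RRT but died first is scored as not requiring it, and that death is charged to the comparison group. At stake is the interpretation of the primary comparison, not the arithmetic of the table.

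**Working it through.** The plan gives no effect size, event count or cohort size, so there is no design figure to reproduce. The one background fraction checks: 174/412 = 42.2% in-hospital mortality among RRT recipients in a cited study (section 5).

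**Effect reading: RRT assumed to have no effect on death or discharge.** Let h and g be the daily hazards of death and of live discharge. With constant hazards, a patient still in hospital eventually dies there with probability P = h / [h + (1 − h)g]. Under no effect, a patient who starts RRT on a given day simply takes on the P of that day. Bias therefore depends on whether P changes over the stay. All hazards below are assumed.

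- Constant ratio (h 1%, g 9%): P = 0.01/(0.01 + 0.99 × 0.09) = 10.1% on every day. No bias.
- Front-loaded deaths (h 2% on days 1-3, then 0.5%; g 12% from day 5): from day 5, P = 0.005/(0.005 + 0.995 × 0.12) = 4.0%, against 10.1% for the whole cohort. Later starters look better.
- Flat deaths (h 1%; g 12% from day 5): from day 5, P = 0.01/(0.01 + 0.99 × 0.12) = 7.8%, against 11.4% overall. Same direction.
- Late deaths (h 0.2% to day 7, then 3%; g 10% from day 3): from day 8, P = 0.03/(0.03 + 0.97 × 0.10) = 23.6%, against 15.0% overall. Later starters look worse.

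An exact day-by-day calculation used three assumed RRT start patterns (1% per day on days 1-7, 2% on days 2-5, 1% on days 3-10):

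| Scenario | Ever/never OR | OR with RRT time-varying |
|---|---|---|
| Front-loaded deaths | about 0.4 to 0.6 | 1.00 |
| Flat deaths | about 0.7 to 0.8 | 1.00 |
| Constant ratio | 1.00 | 1.00 |
| Late deaths | about 1.1 to 1.4 | 1.00 |

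The last column is a day-stratified Mantel-Haenszel ratio. The range is not a bound: a second set of assumed hazards, some more extreme, gave 0.25 to 1.88.

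**Requirement reading.** Inputs:

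- m = 42.2%, mortality in recipients (section 5).
- n = 1% to 10%, share of AKI patients needing RRT (sections 4 and 5).
- b = 5% or 10%, mortality without need (assumed; the documents give no such figure).
- f = share of those needing RRT who die before it starts (assumed; the documents give none).

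Formulas:

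- Mortality in the need group = f + (1 − f)m.
- Mortality in the non-RRT group as coded = [(1 − n)b + nf] / [1 − n(1 − f)].
- Need OR = odds in the need group / odds of b. Coded OR = odds of m / odds in the non-RRT group.

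Example with 1,000 AKI patients, n = 10%, f = 20%, b = 5%. Of the 100 in need, 20 die first and 80 receive RRT. The non-RRT group has 920 patients and 45 + 20 = 65 deaths, or 7.1% instead of 5%. Need-group mortality is 0.20 + 0.80 × 0.422 = 53.8%. The coded OR is 9.62 and the need OR 22.11, a shortfall of 1 − 9.62/22.11 = 56.5%.

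Ranges run over n = 1% to 10%:

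| f | Need-group mortality | Need OR / coded OR, b = 5% | Shortfall | Need OR / coded OR, b = 10% | Shortfall |
|---|---|---|---|---|---|
| 1% | 42.8% | 14.22 / 13.59-13.86 | 2.5-4.5% | 6.74 / 6.51-6.57 | 2.4-3.4% |
| 5% | 45.1% | 15.62 / 12.50-13.75 | 12.0-20.0% | 7.40 / 6.23-6.55 | 11.5-15.8% |
| 10% | 48.0% | 17.55 / 11.37-13.62 | 22.4-35.2% | 8.31 / 5.92-6.51 | 21.6-28.7% |
| 20% | 53.8% | 22.11 / 9.62-13.35 | 39.6-56.5% | 10.47 / 5.38-6.45 | 38.4-48.6% |

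Every coded odds ratio stays well above 1.

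**The case against.** The declared primary objective is an association, and RRT is defined by use. For that question the ever/never table is the right table. This stands, and the point does not challenge it.

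The wording of influence is a stock phrase: section 7.7.2 reuses it for the predictors of CRRT use. Likewise, requirement may be shorthand for use, since Table 7.2 item 15 scores diuretic infusion the same way and no section sets criteria for need apart from receipt. Both remarks are fair. They show that rewording settles much of the matter, not that the wording may stay.

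The sizes rest on assumptions. The hazards and the share dying before RRT are not in the documents, and small shares give small shortfalls. The f = 20% case implies that 0.20/0.538 = 37% of need-group deaths precede RRT. This stands too, which is why the range starts at f = 1%.

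A time-dependent model does not repair the requirement reading, because a patient who needed RRT and died first still contributes only unexposed time. Nor does it remove confounding by indication: sicker patients start RRT, and severity changes over time. It therefore belongs as a sensitivity analysis.

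Finally, section 7.3 may not be a complete list and the eCRF is not among the documents, so the dates may already be captured. They are not named as analysis variables.

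**Conclusion.** The point holds as a matter of interpretation. The ever/never comparison validly describes mortality by RRT received. It is open to timing bias as a statement about the effect of RRT, and to misclassification as a statement about need. The mechanism follows directly from Tables 7.1 and 7.2; the size does not.

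For the effect reading, the odds ratio under no effect lies between about 0.4 and 1.4 in the main scenarios, with no bias when the death and discharge hazards keep a constant ratio. For the requirement reading, the coded odds ratio is 2-20% lower than the need odds ratio for f = 1-5% and 22-57% lower for f = 10-20%, given 42.2% mortality in recipients, 1-10% needing RRT and an assumed 5-10% mortality without need. The association is attenuated, not reversed.

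A reader might infer three stronger things that the documents do not support:

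- That the primary analysis is invalid. It is not, for an association with RRT received.
- That the coding makes RRT look protective. The direction depends on hazards the documents do not give, and can go either way.
- That timing would explain away a large association. Recipient mortality of 42.2% against 5-10% gives an odds ratio of 13.9 to 6.6, while timing alone reached at most 1.88 in the scenarios tried. Those scenarios are assumed, so this is an indication and not a limit.

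**What to change.** 1. Label the groups RRT received / not received, replace the wording of influence with one of association, and keep the ever/never table and logistic model as descriptive. The relabelling is what resolves the requirement reading.
2. From the records already being abstracted, extract the dates of time zero, RRT start, death and discharge (with times where two fall on the same day). Add a pre-specified sensitivity analysis: a cause-specific Cox model for in-hospital death with RRT as a time-dependent covariate and live discharge as the competing event (censored in this model), adjusted for covariates known at time zero. It corrects timing only and does not support a causal statement.
3. Do not enter prolonged ventilation or prolonged ICU stay (Table 7.2 items 11 and 12) as fixed covariates in the model for RRT. They too can be coded positive only in patients who survive long enough. Report them descriptively under the third secondary objective.
4. State in section 7.8 that the ever/never odds ratio is open to timing bias, and that confounding by indication, including time-varying severity, remains in every model.
5. Reconcile two pairs of passages so that time zero and the groups are defined. Section 7.2.1 identifies AKI by a creatinine value "which was checked within 12 hours post-surgery", while Table 7.2 item 1 sets no such limit and adds "with urine output < 0.5 cc/kg/hour for 6 consecutive hours". Section 7.7.2 names the groups by CRRT, while Table 7.2 item 2 also counts intermittent dialysis.

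The cost is a few dates per patient (total workload unknown, because section 7.5 states no cohort size), one more model and some rewording. The hazard ratio is a different measure from in-hospital risk; it sits beside the planned comparison and does not replace it.

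### Age is known in years but is analysed only as over 60 versus 60 or younger, without a reason, so the adjusted RRT odds ratio can keep residual age confounding

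*Combined protocol and SAP*

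**What the plan says.** Table 7.2 item 3 (section 7.3.1) defines age as "calculated from the day of birth to the day the surgery was performed in years" and scores it "0 = ≤ 60 years 1 = > 60 years", on a categorical scale. No other analysis form of age appears. Section 7.7.2 mentions means, SDs and medians for continuous variables, but only as descriptive statistics.

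The only reason offered for categorising is in section 7.3: "For the study's purpose, several continuous variables are categorized qualitatively such as mechanical ventilation (>48 hours as a cutoff point". Age is not among the examples listed there, and nothing explains the choice of 60.

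Section 7.7(c) explains the model: "Because the independent variables are categorical, logistic regression was used for the analysis". Section 7.7.2 describes the steps for the primary outcome: "Bivariate analysis was carried out using the chi square/fisher's exact test to see whether there was a difference in the incidence of death", then a variable moves on under the rule "which was then continued to the multivariate analysis stage if it had a p value <0.25", then "regression multiple logistics with a significance level of 0.05". The same sequence is set out for the second model, in which the outcome is use of CRRT.

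**The concern.** The primary comparison, death in hospital with and without RRT, is not randomised, so its credibility rests on adjustment. Age is fixed before RRT starts, may be related to both RRT and death, and is also a candidate factor under the third secondary objective. Section 7.2.1 sets a lower age limit ("Target population for this study is patient aged at least 18 years") and no upper one. Patients of 20 and 59 therefore share one code, and patients of 61 and 82 share the other. If risk rises within those groups, the part of age that the code misses can stay in the RRT odds ratio, and the test of age itself is weaker. A weaker test also makes it more likely that age fails the p < 0.25 screen.

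**Working it through.** **Inputs.** From the documents: the cut at 60, the lower age limit of 18, the p < 0.25 screen and the 0.05 level. They give no mean or SD of age, no share above 60, no age effect, no sample size and no expected RRT odds ratio. There is no figure of the plan's to reproduce, and every size below rests on stated assumptions.

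**1. Age information lost.** Loss = 1 − r², where r is the correlation between age and the over-60 indicator. For normal ages, c = (60 − mean)/SD, p = 1 − Φ(c) and r² = φ(c)² / [p(1 − p)]. With SD 12:

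- Mean 60: c = 0, p = 0.500, r² = 0.1592/0.2500 = 0.64, loss 36%.
- Mean 56: c = 0.333, p = 0.369, r² = 0.1424/0.2330 = 0.61, loss 39%.
- Mean 52: c = 0.667, p = 0.252, r² = 0.1020/0.1887 = 0.54, loss 46%.

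Under normality 36.3% is the minimum, reached when half the patients are over 60. Other assumed distributions give 25.9% (uniform 35–80), 29.8% (uniform 18–85), 41.1% and 48.0% (two mixtures of younger and older patients) and 73.1% (normal, mean 45, SD 10).

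**2. Confounding left in the RRT odds ratio.** Let b be the RRT log odds ratio from a logistic model with no age term (crude), with the over-60 code (binary) or with age in years (linear). Residual share = (b_binary − b_linear)/(b_crude − b_linear).

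The base case was simulated with 1,000,000 patients per scenario: normal ages with mean 52–60 and SD 12, log-odds per decade of 0.2–0.4 for RRT and 0.3–0.6 for death, RRT in about 7%, true RRT odds ratio 4. One scenario gave 4.90 crude, 4.26 binary and 3.96 linear:

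- Share left: ln(4.26/3.96)/ln(4.90/3.96) = 0.0730/0.2130 = 34%.
- Inflation relative to age in years: 4.26/3.96 = 1.08.

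Over the whole base case the share left is 33–41% and the inflation factor 1.02–1.085.

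**3. Wider assumptions.** Selected simulations with about 1.5–2 million patients each. The second column gives the odds ratios per decade of age for RRT and for death.

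| Age distribution | RRT / death | True RRT OR | Crude | Over-60 code | Age in years | Share left |
|---|---|---|---|---|---|---|
| Normal 60, SD 10 | 1.3 / 1.5 | 1 | 1.107 | 1.041 | 1.002 | 39% |
| Normal 55, SD 12 | 1.5 / 1.8 | 1 | 1.352 | 1.109 | 0.998 | 35% |
| Normal 55, SD 12 | 1.5 / 1.8 | 6 | 7.048 | 6.376 | 6.017 | 37% |
| Normal 45, SD 12 | 2 / 2 | 1 | 1.786 | 1.298 | 1.012 | 44% |
| Normal 45, SD 12 | 1.3 / 1.5 | 6 | 6.426 | 6.250 | 5.995 | 60% |
| Uniform 18–85 | 1.5 / 1.8 | 1 | 1.847 | 1.152 | 0.996 | 24% |

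The share left is not the size of the bias. The 60% row has an inflation of 6.250/5.995 = 1.04, while the 24% row has 1.152/0.996 = 1.16. When the true odds ratio is 1, the over-60 model gave about 1.04–1.30 across all the runs.

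**4. Limiting cases.** If risk changes only by a step at 60, the code loses nothing. If age is unrelated to RRT or to death, there is no age confounding to leave. If age fails the screen, the crude column applies: in the base-case example 4.90 instead of 4.26, which is 4.90/3.96 = 1.24 times the value with age in years.

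**5. The sentence in 7.7(c).** It argues from the coding of the predictors to the choice of model. The outcome in Table 7.1 is died or not died; that is what calls for logistic regression, which takes continuous predictors directly.

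**The case against.** **The reason for the cut.** A reader might infer that age was cut because the authors believed that logistic regression needs categorical predictors. The documents do not say so. Section 7.7(c) goes from categorical predictors to logistic regression, not the reverse, and section 7.3 gives only a general study purpose for categorising. The sentence in 7.7(c) is a separate error, not the motive for the age code.

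**The figures.** A reader might also take it as fact that over a third of the age information is lost and about a third of the confounding stays. Those figures belong to normal ages cut near their median with linear effects. The population mixes coronary, valve and adult congenital surgery from age 18, so normality is not assured; uniform ages lose 26–30%.

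**The consequence.** An inflation of 2–9% on an odds ratio near 4 would hardly change the primary reading. The simulations adjust for age alone; diabetes, hypertension, renal history and type of surgery may also be in the model and could absorb part of the residual, which was not examined. The documents do not support a claim that the coding would overturn the primary result.

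All of this stands, and it limits the size of the point. It does not supply a reason for the cut at 60, and the plan has no analysis that would show whether the cut matters.

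**Conclusion.** The point holds in a limited form. Age is available in years, is analysed only in two groups without a rationale, and no continuous-age analysis is planned. This loses information and can leave residual age confounding in the adjusted RRT odds ratio. The base-case sizes (36–46% of age variance lost, 33–41% of age confounding left, odds ratio inflated by about 2–9%) assume normal ages with mean 52–60 and SD 12, linear effects on the log-odds scale and a true RRT odds ratio of 4. Other age distributions and means widen the ranges to 26–73% lost and 24–60% left, and both can be zero.

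These figures apply only if age passes the p < 0.25 screen. If it does not, the model has no age term and all the age confounding remains, apart from whatever correlated covariates take up.

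The reason given for logistic regression in 7.7(c) is wrong whatever is decided about age. The change is worth making because it is almost free, not because the expected bias is large.

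**What to change.** In Table 7.2 item 3 and sections 7.7(c) and 7.7.2:

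- Enter age in years as a linear term in both logistic models (death, and use of CRRT). Allow a quadratic term or a restricted cubic spline only if the number of events permits.
- Include age in the primary RRT–mortality model regardless of the p < 0.25 screen.
- For the bivariate result for age, use univariable logistic regression, or a t-test or Mann-Whitney test. The chi-square and Fisher tests now specified cannot take age in years.
- Keep the over-60 grouping for the descriptive table only.
- Replace the sentence in 7.7(c) with: *Because the outcome is binary, logistic regression is used; age is entered in years.* This wording is confined to age on purpose. A general rule for continuous variables would silently override the creatinine > 3.0 mg/dL coding in item 7, which needs its own decision.

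**Cost.** Wording only, with no new data, since age in years is already derived. A linear term uses one degree of freedom, the same as the present code. A quadratic adds one, and a 3–4 knot spline uses 2–3 in all, which is why these depend on the event count. Section 7.7.2 foresees a SAP finalised before database lock, and the change belongs there.
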